4.1.2. Two-stage Design for Part C

Part C consists of two stages to first evaluate the safety and tolerability and then the anti-tumor activity of abemaciclib in combination with chemoimmunotherapy. The design is briefly described below with a figure immediately following.

Stage 1

Stage 1 starts with a dose optimization to identify MTD. Specifically, it will initially enroll 3 patients at 55 mg/m² (i.e., the MTD for abemaciclib in combination with irinotecan and temozolomide in Part A plus dinutuximab and GM-CSF) and use 3+3 rules to guide dose decision. During MTD identification, if 55mg/m² is deemed intolerable, then a lower abemaciclib dose of 30mg/m² (keeping the other drugs the same) will be explored. If this lower dose level is deemed intolerable, Arm C will be terminated due to intolerance.

In addition to the safety assessment, the anti-tumor activity will be measured by objective tumor response. If MTD is declared, an expansion cohort will enroll at the MTD to confirm the tolerability while evaluating the preliminary anti-tumor activity. In the expansion cohort, up to [REDACTED] patients may be simultaneously enrolled. Stage 1 will enroll up to [REDACTED] DLT-evaluable patients at the identified MTD. If none of the following stopping rules are triggered, the MTD will be confirmed as RP2D and Part C will move to Stage 2.

- Rule A: stop for toxicity if [REDACTED] CCI of the DLT-evaluable patients experience DLT.
- Rule B: stop for intolerance if [REDACTED] CCI patients discontinue due to treatment-related AE before completing [REDACTED] cycles.

- Rule C: stop for insufficient evidence of anti-tumor activity if < ^{cc1} of ^{cc1} patients are responders (i.e., have objective tumor response, including a best overall response of complete response [CR], partial response [PR] or minor response [MR] per INRC).

De-escalation during cohort expansion: If 55mg/m² is declared the MTD, but either stopping Rule A or B is triggered in the cohort expansion, subsequent patients will be treated at 30mg/m² and those at the 55 mg/m² dose may be dropped to 30 mg/m² upon investigator's discretion. Part C will continue to enroll until there are ^{cc1} total patients treated at 30 mg/m² with a minimum of ^{cc1} newly enrolled DLT-evaluable 30mg/m² patients. If no stopping rules are triggered, the dose combination with abemaciclib at 30 mg/m² is the RP2D and Part C will move to Stage 2.

Stage 2

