9.5. Interim Analyses

Data will be reviewed on a cohort-by-cohort basis during the study, until the MTDs (not to exceed 115 mg/m² BID) are determined for Parts A and B or CCI [REDACTED]. The purpose of these reviews is to evaluate the safety data at each dose level and determine if a DLT has been

observed that would suggest the MTD for each cohort has been met or exceeded in the dose finding portion. The investigators and Lilly study team will make the determination regarding dose escalation based upon the review of the safety and tolerability data as described in this protocol.

During the dose-expansion portion of each study part, interim analyses may be conducted to review available safety, PK, and efficacy data.

CCI

██████████ DMC will conduct the first interim analysis approximately 2 months (or earlier if deemed appropriate) after Stage 1's last patient begins Cycle 1. If any of the following stopping rules are met or a significant safety signal is identified, the DMC may recommend termination of enrollment, and/or termination of study treatment.

- Rule A: stop for toxicity if ██████ CCI of the DLT-evaluable patients experience DLT.
- Rule B: stop for intolerance if ██████ CCI patients discontinue due to a treatment-related AE before completing ██████ cycles.
- Rule C: stop for insufficient evidence of anti-tumor activity if ██████ of the ██████ patients are responders (i.e., have objective tumor response, including a best overall response of complete response [CR], partial response [PR] or minor response [MR] per INRC).

If 55 mg/m² is declared the MTD, but either Rule A or B is triggered during cohort expansion, the DMC may recommend that subsequent patients be treated at 30 mg/m². See Section 4.1.2.

The DMC will meet and review the overall safety and efficacy data approximately every 6 months thereafter while patients remain in the study. At the recommendation of the DMC, the frequency of safety interim analyses may be modified. See Section 10.1.4 for further details.

Other interim analysis may be added as deemed appropriate by the sponsor.

10. Supporting Documentation and Operational Considerations

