**Abemaciclib (LY2835219)**

Study I3Y-MC-JPCS is a multicenter, non-randomized, open-label, Phase 1b dose-escalation study comprised of 2 parts of 3+3 dose escalation of abemaciclib in pediatric patients with relapsed/refractory solid tumors. Part A will test abemaciclib in combination with irinotecan and temozolomide. Part B will test abemaciclib in combination with temozolomide. Part C will test abemaciclib in combination with dinutuximab, GM-CSF, irinotecan, and temozolomide.

Eli Lilly and Company  
Indianapolis, Indiana USA 46285  
Protocol I3Y-MC-JPCS  
Phase 1b/2

Document ID: VV-CLIN-072195

LY2835219

Approved on 30 Nov 2022 GMT

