#### **Stage 1**

Stage 1 starts with a dose optimization to identify MTD. Specifically, it will initially enroll 3 patients at 55 mg/m^2 (that is, the MTD for abemaciclib in combination with irinotecan and temozolomide in Part A plus dinutuximab and GM-CSF) and uses 3+3 rules to guide dose decision. During MTD identification, if 55mg/m^2 is deemed intolerable due to DLT, then a lower dose of 30mg/m^2 (that is, reduce abemaciclib to 30mg/m^2 while keeping the other drugs the same) will be explored. If this lower dose level is deemed intolerable, Arm C will be terminated due to intolerance.

In addition to the safety assessment, the anti-tumor activity will be measured by objective tumor response. If MTD is declared, an expansion cohort will be enrolled at the MTD to further confirm the tolerability while evaluating the preliminary anti-tumor activity. In the expansion cohort, up to 5 patients may be simultaneously enrolled. Stage 1 will enroll up to CCI DLT-evaluable patients at the identified MTD. If none of the following stopping rules are triggered, the MTD will be confirmed as RP2D and Part C will move to Stage 2.

- Rule A: stop the trial for toxicity if CCI of the DLT-evaluable patients experience DLT.

- Rule B: stop the trial for intolerance if **CCI** patients discontinue due to treatment-related AE before **cc** cycles.
- Rule C: stop for insufficient evidence of anti-tumor activity if **<cc** of the **cc** patients are responders (that is, have objective tumor response, including a BOR of CR, PR, or MR per INRC).

**De-escalation during cohort expansion:** If 55mg/m^2 is declared as the MTD, and any stopping rule is triggered during cohort expansion on this dose level, subsequent patients will be treated at 30mg/m^2. Patients in the cohort expansion for 55 mg/m^2 may be moved to 30 mg/m^2 upon investigator's discretion. Part C will continue to enroll patients until there are **cc** patients treated on 30 mg/m^2, including newly enrolled patients and those moved from the 55 mg/m^2. For the new patients, a minimum of **cc** DLT-evaluable patients are required. If none of the stopping rules are triggered, the dose combination with abemaciclib at 30 mg/m^2 is the RP2D and Part C will move to Stage 2.

## Stage 2

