When Part C moves to Stage 2, an additional **cc** patients will be enrolled at the RP2D. Among the **cc** evaluable patients treated in Stages 1 and 2 at the RP2D, if there are **CCI** responders, then there is insufficient evidence of anti-tumor activity. If **CCI** of the patients are responders, then it is reasonable to conclude that the drug combination has promising anti-tumor activity that could warrant further study.

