## 6.3. Sample Size Determination

Approximately 30 to 117 patients will be enrolled in this Phase 1b/2 study, with 24 to 60 in Parts A and B and 6 to 57 in Part C. The sample size for Parts A and B is primarily determined by DLTs (up to 6 evaluable patients at a dose level before establishing the MTD), while the sample size for Part C depends on both DLTs and responses. The maximum sample size of 57 in Part C is determined by considering dose finding and ensuring that 46 patients are treated on the RP2D. The sample size of **CCI** is determined using Simon's optimal 2-stage design with a power of 80% and a one-sided type I error rate of 0.025, given a null ORR of **CCI** against an alternative ORR of **CCI** assumed at the RP2D.

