### 7.3.1. *Primary Efficacy Endpoints*

The study was not designed to make an efficacy assessment in Parts A and B, while ORR will be assessed as co-primary endpoint in Part C if a RP2D is achieved. In Part C, ORR is the percentage of patients with a BOR  $\geq$  PR (CR, PR, and MR) per INRC (Park et al. 2017). The response criteria integrate the responses of all lesions using computed tomography/magnetic resonance imaging and/or MIBG/fluorodeoxyglucose-positron emission tomography lesions, and assessment of bone marrow disease. Details are provided in Protocol Section 9.4.6.2.1. All time point responses observed while on study treatment and during short-term follow-up, but before the initiation of post-discontinuation therapy, will be included in the derivation. The primary analysis of response will be based on confirmed responses as defined in [Table JPCS.7.2](#). However, summaries including unconfirmed responses will also be provided. For the interim analysis for Part C, unconfirmed responses may be used.

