### 7.7.2. Part C

In addition to regular cohort-by-cohort analyses for the dose escalation/de-escalation, an interim analysis for both safety and efficacy is planned for Part C, given that MTD is declared in Stage 1. Specifically, after the MTD is established, an expansion cohort will be enrolled at the MTD to further confirm the tolerability while evaluating the preliminary antitumor activity. In the expansion cohort, up to [REDACTED] patients may be simultaneously enrolled. Stage 1 will enroll up to [REDACTED] DLT-evaluable patients at the identified MTD. The interim analyses will be triggered with data cutoff approximately 1 month (or earlier if deemed appropriate) after the last DLT-evaluable patient begins Cycle 2. If none of the following stopping rules are triggered, the MTD will be confirmed as RP2D, and Part C will move to Stage 2.

- Rule A: stop the trial for toxicity if  $\geq$  [REDACTED] of the DLT-evaluable patients experience DLT.
- Rule B: stop the trial for intolerance if  $\geq$  [REDACTED] patients discontinue due to treatment-related AE before [REDACTED] cycles.
- Rule C: stop for insufficient evidence of anti-tumor activity if  $<$  [REDACTED] of the [REDACTED] patients are responders (that is, have objective tumor response, including a BOR of CR, PR or MR per INRC).

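### SAP 6.1.2 sends Part C to 30 mg/m² after any stopping rule, futility Rule C included; the protocol does so only after Rule A or B

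*SAP*

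**What the plan says.** Stage 1 of Part C has three stopping rules at the MTD: Rule A counts DLTs, Rule B counts discontinuations for treatment-related adverse events, and Rule C requires a minimum number of responders. Their thresholds are redacted. The text on what follows is not.

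- SAP 6.1.2, de-escalation paragraph: if 55 mg/m² is the MTD "and any stopping rule is triggered during cohort expansion on this dose level, subsequent patients will be treated at" 30 mg/m². If no rule then fires at 30 mg/m², that dose becomes the RP2D and Part C enters Stage 2.
- Protocol 4.1.2, same paragraph: the move follows if 55 mg/m² is the MTD "but either stopping Rule A or B is triggered in the cohort expansion".
- Protocol 9.5: the DMC may recommend 30 mg/m² if 55 mg/m² is the MTD "but either Rule A or B is triggered during cohort expansion". If any of the three rules is met, the DMC may recommend ending enrolment or treatment.
- SAP 7.7.2 lists the same three rules and then gives only the favourable branch: "If none of the following stopping rules are triggered, the MTD will be confirmed as RP2D, and Part C will move to Stage 2". It does not say what follows each rule.

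SAP 6.1.2 (Stage 2) attaches one conclusion to success at whichever dose is the RP2D: "promising anti-tumor activity that could warrant further study". SAP 6.3 sets one Simon optimal design at the RP2D, with one-sided error 0.025 and power 80%, and says the "maximum sample size of 57 in Part C is determined by considering dose finding and ensuring that 46 patients are treated on the RP2D".

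**The concern.** The two documents give different instructions after the same result. If too few patients respond at 55 mg/m² and toxicity is acceptable, the protocol has no path to 30 mg/m², while the SAP sends the next patients there.

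ORR is a co-primary endpoint in Part C. A Simon design holds its error rate because failing Stage 1 ends the test. If failure instead restarts the same test at a lower dose, the combination gets a second chance at the same claim. Neither document adjusts for that. It would also mean enrolling more children after a futility result, and the documents give no reason why a lower dose should do better on response.

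**Working it through.** **Inputs from the documents.** One-sided error 0.025, power 80%, Simon's optimal design, 46 patients at the RP2D, maximum 57 (SAP 6.3). The null and alternative ORR, the Stage 1 size and the cut-offs are redacted.

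**Assumptions.** Null 42%, alternative 65%; both doses null; a fresh set of patients at 30 mg/m², so no responses carried over from 55 mg/m²; Rules A and B independent of response.

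**Step 1: the plan's own figure.** The 46 cannot be strictly reproduced with the rates redacted, but it is attainable. For 42% against 65%, the optimal design stops if 5 or fewer of 11 respond and claims activity if more than 25 of 46 respond. Exact binomial: error a = 0.0246, power 0.802, n = 46.

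**Step 2: how often Rule C fires under the null.** PET = P(X ≤ 5 | 11, 0.42) = 0.7076.

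**Step 3: Rules A and B never fire.**
- Protocol wording: a = 0.0246, or 0.025.
- SAP wording: a + PET × a = 0.0246 + 0.7076 × 0.0246 = 0.0246 + 0.0174 = 0.0420.

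**Step 4: chance q = 0.2 of Rule A or B at each dose (assumed).**
- Protocol wording: (1−q)a + q(1−q)a = 0.0197 + 0.0039 = 0.0236, or 0.024.
- SAP wording adds (1−q)² × PET × a = 0.64 × 0.0174 = 0.0111, giving 0.0347, or 0.035.

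**Step 5: range over other assumed rates.** With nulls of 30–50% and differences of 20–25 points, eight optimal designs have n = 46. The fourth column takes a complete fresh test at 30 mg/m². The last column holds Part C to 57 patients by assuming that n1 − 11 patients (n1 being the Stage 1 size) move at random from 55 mg/m² and keep their response status.

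| Null / alternative | Stage 1 | Final | Either-dose error, fresh test | Patients (n1 + 46) | Error held to 57 |
|---|---|---|---|---|---|
| 36 / 59% | 7/16 | 22/46 | 0.0448 | 62 | 0.0405 |
| 40 / 63% | 7/15 | 24/46 | 0.0442 | 61 | 0.0405 |
| 40 / 64% | 5/11 | 24/46 | 0.0411 | 57 | 0.0411 |
| 42 / 65% | 5/11 | 25/46 | 0.0420 | 57 | 0.0420 |
| 46 / 68% | 7/14 | 27/46 | 0.0417 | 60 | 0.0387 |
| 46 / 70% | 7/13 | 27/46 | 0.0368 | 59 | 0.0352 |
| 48 / 70% | 8/15 | 28/46 | 0.0396 | 61 | 0.0362 |
| 48 / 71% | 7/13 | 28/46 | 0.0373 | 59 | 0.0356 |

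The range is 0.037–0.045, or 0.035–0.042 held to 57. With q = 0.2 and the 57 limit, the SAP wording gives 0.029–0.035 and the protocol wording 0.020–0.024. Two complete independent tests at 0.025 cannot exceed 1 − 0.975² = 0.0494. The capped values depend on random movement; the SAP moves patients at the investigator's discretion and requires a redacted minimum of new ones, so some of these cases may not be permitted.

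**The case against.** The strongest reply is that nobody intends a futility-triggered dose reduction. Wherever a reason for 30 mg/m² is given, it is tolerability: the Part C dosing footnotes in protocol 1.1 and 6.1, protocol 4.3.1, and the MTD step in SAP 6.1.2. Rule C is itself worded as a stop, and the SAP runs its interim after the last DLT-evaluable Stage 1 patient has begun Cycle 2, arguably after expansion rather than during it. This stands as evidence of intent and limits the practical risk. It does not cure the text. In SAP 6.1.2, Rules A and B are also worded as stops, yet they lead to 30 mg/m², and all three rules are judged at the same interim.

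A second reply is that the SAP merely predates the current protocol. Its cover reads "Approved on 30 Nov 2022 GMT", its revision history ties version 2 to Amendment (e), and the Rule A or B sentence in protocol 9.5 came with Amendment (f). But for the de-escalation text in 4.1.2, the (f) log records only a changed conjunction, so the restriction was probably already in (e). That is an inference: the text of (e) is not available and the log omits minor edits. Either way, the documents now disagree.

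A third reply is that neither document states an error standard across doses; 0.025 is set at the RP2D. This is correct. The excess concerns declaring the combination active at either dose, in a single-arm study whose positive conclusion is only that further work is warranted.

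Three stronger readings are tempting and not supported:

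- **That the sponsor chose a second test.** No text gives a rationale for one. That 11 + 46 = 57 matches the maximum under one assumed design proves nothing, since a move after Rule A or B needs the same number.
- **That the test at 55 or at 30 mg/m² is itself inflated.** Without carry-over, each is at most 0.025.
- **That the protocol wording guarantees 0.025.** It also lets moved patients count at 30 mg/m². For 42% against 65%, q = 0.2, and three moved patients taken responders first (an extreme assumption), the protocol wording gives 0.032. Separately, SAP 7.3.1 says: "For the interim analysis for Part C, unconfirmed responses may be used". With an interim response rate 5 or 10 points above the null, the protocol wording gives 0.027 or 0.029 and the SAP wording 0.043 or 0.042. The excess over 0.025 under the protocol wording has nothing to do with the de-escalation trigger.

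**Conclusion.** This is an inconsistency between SAP and protocol, most likely a drafting error and not a design decision. The words that conflict are visible, so redaction does not explain it. Under the stated assumptions, the direction is certain: a further chance to pass after a futility failure can only raise the probability of a false claim of activity at one dose or the other.

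The size is an illustration. It rests on assumed response rates, on both doses being null, on Rules A and B being independent of response and, for the 42%/65% figures in Steps 3 and 4, on no responses being carried over from 55 mg/m². It is material against a nominal 0.025 but below 0.05. The practical risk is limited because the protocol names only Rules A and B, but a co-primary endpoint should not have two different stopping consequences in force.

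**What to change.** In SAP 6.1.2, replace 'any stopping rule' in the de-escalation paragraph with 'either Rule A or Rule B'. State there and in SAP 7.7.2 that Rule C does not lead to 30 mg/m² but to stopping for insufficient activity, subject to the DMC recommendation described in protocol 9.5. A flat statement that Rule C ends Part C would be firmer than protocol 9.5, where the DMC may recommend termination. While the paragraph is open, it would help to say how patients moved from 55 mg/m² count towards ORR at 30 mg/m².

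The cost is a few words in two SAP sections, with no additional patients and no protocol amendment.

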## **7.2. Safety Analyses**

Safety analyses will be completed as specified below, unless COVID-19 impact creates a situation requiring a change to an existing analysis or a need for additional analyses as outlined by Nilsson et al. (2020).

Safety analyses will be based on the safety population, unless otherwise stated, and summarized by cohort corresponding to the actual regimen received at first dose. Additionally, all patients assigned to the RP2D (for example, the applicable cohort from dose escalation and the dose expansion cohort) within each study part may be aggregated and summarized together.

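### After de-escalation in Part C, patients moved from 55 to 30 mg/m² can count as 30 mg/m² patients in Rule C and the final response rate

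*SAP*

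**What the plan says.** Part C runs a Simon optimal two-stage design with dose finding inside Stage 1. SAP 6.3 describes a "design with a power of 80% and a one-sided type I error rate of 0.025", and sizes Part C by "ensuring that 46 patients are treated on the RP2D", with a Part C maximum of 57.

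If 55 mg/m² is declared the MTD but a stopping rule is met in the expansion, new patients start at 30 mg/m². Under Protocol 4.1.2, "those at the 55 mg/m² dose may be dropped to 30 mg/m²" at the investigator's discretion. Enrolment continues until a fixed (blacked-out) total has been treated at 30 mg/m². SAP 6.1.2 says who makes up that total: "including newly enrolled patients and those moved from the 55" mg/m² dose. The protocol has the same structure, a total at 30 mg/m² with a minimum newly enrolled. In both documents the minimum of new patients is stated for DLT-evaluable patients only.

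If no rule is then triggered, 30 mg/m² is the RP2D, and the final decision is read on the "evaluable patients treated in Stages 1 and 2 at the RP2D" (SAP 6.1.2, Stage 2).

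For response, Protocol 9.4.6.2.1 takes the best response at any time point, and SAP 7.3.1 uses all time points on study treatment and in short-term follow-up. Neither restarts baseline, response or cycle count when the dose changes.

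Elsewhere the SAP attributes patients differently. Section 7.2 has safety "summarized by cohort corresponding to the actual regimen received at first dose", and section 7.3 allows pooling of patients assigned to the RP2D.

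**The concern.** The Part C objective is to find the RP2D and estimate anti-tumor activity at that dose. The two-stage error rates assume that everyone counted was treated at that dose from the start and was not chosen on outcome. Moved patients break both assumptions.

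- **Carry-over.** A response first seen at 55 mg/m² remains the patient's best overall response and can be counted for 30 mg/m².
- **Selection.** Study treatment ends at progression or unacceptable toxicity, so early failures at 55 mg/m² cannot be moved. The investigator, who also assesses response in this open-label study, chooses among those who remain.

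At stake are the Stage 1 activity gate (Rule C) and the co-primary ORR, which could credit 30 mg/m² with activity it did not produce. The three attribution rules in the SAP (treated at, regimen at first dose, assigned to) would also place the same moved patient in different dose groups in different tables.

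**Working it through.** **1. The plan's own figure.** N = 46 cannot be strictly reproduced, because both response rates are blacked out. An exact search for Simon's optimal design at one-sided 0.025 and 80% power gives N = 46 for several assumed pairs:

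| Null vs alternative | Pass Stage 1 if | Positive if | Alpha | Power | Pass Stage 1 under null |
|---|---|---|---|---|---|
| 0.40 vs 0.63 | >7/15 | >24/46 | 0.0247 | 0.808 | 0.213 |
| 0.42 vs 0.65 | >5/11 | >25/46 | 0.0246 | 0.802 | 0.292 |
| 0.20 vs 0.41 | >4/16 | >14/46 | 0.0222 | 0.806 | 0.202 |

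So 46 is attainable. For context, Protocol 2.2 gives a response rate of 41.5% for the backbone regimen. The steps below use 0.40 vs 0.63 as the illustration.

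**2. Model.** Of the 15 Stage 1 patients counted at 30 mg/m², m were moved and respond with probability q. The other 15 − m, and all 31 in Stage 2, respond at the null of 0.40. With X1 the sum of Binomial(m, q) and Binomial(15 − m, 0.40):

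false-positive risk = Σ over x > 7 of P(X1 = x) × P(Binomial(31, 0.40) > 24 − x).

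**3. Selection only, with 55 mg/m² also at 0.40.** If a share f of all 55 mg/m² patients has left without response, q = 0.40/(1 − f). As a share of non-responders this is f/0.60.

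- 20% of non-responders gone: f = 0.12, q = 0.40/0.88 = 0.455.
- 20% of all gone (0.20/0.60 = 33% of non-responders): q = 0.40/0.80 = 0.50.
- 40% of all gone (0.40/0.60 = 67% of non-responders): q = 0.40/0.60 = 0.67.

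| Already left without response | m = 1 | m = 3 | m = 5 | m = 8 | Pass Rule C, m = 5 |
|---|---|---|---|---|---|
| none | 0.025 | 0.025 | 0.025 | 0.025 | 0.21 |
| 20% of non-responders | 0.026 | 0.029 | 0.031 | 0.036 | 0.26 |
| 33% of non-responders | 0.027 | 0.032 | 0.037 | 0.047 | 0.30 |
| 67% of non-responders | 0.031 | 0.046 | 0.066 | 0.108 | 0.46 |

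**4. Carry-over only.** If 55 mg/m² is truly active (q = 0.63) and nobody has left, five moved patients give 0.059.

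**5. Sensitivity to the assumed design.** With five moved and 20% of all patients gone, 0.42 vs 0.65 gives 0.038 and 0.20 vs 0.41 gives 0.029.

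**6. Rule B.** Assume a limit of at least 4 of 11 and a true discontinuation rate of 30%. The chance of triggering is 0.43 with all new patients, and 0.24 if five moved patients carry half that risk. If the patients moved are those tolerating 55 mg/m² poorly, the shift is smaller or reversed.

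**The case against.** The strongest reply has five parts.

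- **Carry-over is inferred.** No sentence says that a response at 55 mg/m² counts for 30 mg/m². SAP 7.3 speaks of patients assigned to the RP2D, which can be read as leaving moved patients out. This stands as far as it goes. But the Stage 2 text counts patients treated at the RP2D, and the response rules have no reset, so following them as written gives the carry-over. The two readings conflict, which is itself the defect.
- **A moved patient may bring no response.** Rule A can trigger on Cycle 1 DLTs, before the first scan at the end of Cycle 2. True in that case. Selection by early departure can still operate.
- **The number moved is capped.** The minimum of new patients limits m, and it is blacked out, so m = 5 or 8 may be impossible. This stands.
- **The direction may differ.** The SAP de-escalates on any stopping rule, Rule C included. A 55 mg/m² cohort that failed Rule C is short of responders, which could offset the bias. The protocol names Rule A or B only. The SAP was written for Amendment (e) and the protocol is at Amendment (f), so the passages must be reconciled.
- **The branch is contingent.** It needs an MTD of 55 mg/m², a trigger in the expansion, patients moved, and 30 mg/m² cleared. A data monitoring committee reviews the interim, and a positive result supports only further study. This lowers the severity.

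A reader might also infer that Rule A is compromised and that Rule B is biased in favour of 30 mg/m². The documents do not support either. Rule A is largely protected by the minimum of new DLT-evaluable patients, and the direction for Rule B is not established.

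**Conclusion.** The point holds for Rule C, the final responder count and the co-primary ORR at 30 mg/m². As written, the plan can count responses seen at 55 mg/m², and a group selected for still being on treatment, as evidence for 30 mg/m². Its attribution rules also disagree with one another.

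The size is not known. Under 0.40 vs 0.63 with five moved patients and selection alone, the false-positive risk is 0.031 to 0.066 against 0.0247. With one moved patient it is about 0.027 when 20% of all patients had left. A reader might take 0.108 from the table as the expected inflation. It requires 8 of 15 places filled by moved patients and two-thirds of non-responders already gone, and the documents support neither assumption.

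This is a should-fix: the correction is cheap and specific, but the issue arises only if de-escalation happens and patients are moved. The rule needs to be set before then, because afterwards the responses of the moved patients would be known.

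**What to change.** In Protocol 4.1.2 and SAP 6.1.2, 7.3.1 and 7.7.2:

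1. State that Rule C, the final responder count and the primary ORR at 30 mg/m² use only patients whose first abemaciclib dose was 30 mg/m².
2. Report moved patients with the 55 mg/m² cohort, as SAP 7.2 already does for safety, and show their data after the switch separately. Give an ORR that includes them as a sensitivity analysis.
3. Apply the same attribution to Rule B, or report Rule B with and without moved patients.
4. If the 57-patient ceiling leaves fewer than 46 at 30 mg/m², prespecify that the final cut-off is recomputed for the number attained at one-sided 0.025, and restate the power.
5. Reconcile the de-escalation trigger between the SAP (any stopping rule) and the protocol (Rule A or B).

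The investigator's freedom to move patients is untouched. The cost is wording, and some power if this branch is reached. If 11 patients had started at 55 mg/m², 57 − 11 = 46 and nothing is lost. If 15 had, 57 − 15 = 42 remain. Under 0.40 vs 0.63, with Stage 1 kept at >7/15, the final cut-off becomes >23/42 (alpha 0.015; >22/42 would give 0.028), and power falls from 0.81 to 0.75.
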